18 BLINDING AND CODE BREAKING

18.1 Blinding

Participants and their parents cannot be blinded to their treatment. The treating clinician also cannot be blinded to the treatment they are providing. However, the clinical team will not be involved in any part of the follow-up assessment of the participants. The patient reported outcome data will be collected directly from the participants and their parents. The radiographic outcomes will be determined by an independent assessor blinded (where possible) to the interventions.

Table 10 provides an overview of the blinding status of all individuals involved in the conduct and management of the study.

Table 10: Blinding status of those involved in study conduct and management.

| Role in study | Blinding status | Additional information |
|----------------------|-----------------|--|
| Participants/parents | Not blinded | It is not possible to blind due to nature of the intervention. |
| | | Participants will be told their treatment allocation immediately |
| | | after randomisation. |

| Site research staff including Principal Investigator | Not blinded | Not possible due to the nature of the intervention. Following randomisation, an email will be sent to the PI (unblinded only for participants they randomise at their own site) and/or member of the site research team performing the randomisation (as delegated) confirming treatment allocation. |
|--|------------------------|--|
| CI | Blinded for | The CI will remain blinded to treatment allocation overall |
| | those at sites | (knowledge of treatment allocation is limited to participants at |
| | other than their | their own site). In instances where serious adverse events are |
| | own, except for | reported, the CI will become unblinded to complete the full |
| | any SAE | causality assessment. |
| | causality | |
| | assessment | |
| Database | Not blinded | The database programmer is responsible for the management of |
| programmer | | randomisation system and the REDCap database and will have |
| | | access to all unblinded datasets. |
| OP Non-STOP Study | Not blinded | Study Management staff within OP Non-STOP will not be blinded |
| Management staff | | to treatment allocations as site staff may require support for |
| | | randomisation, or participants may contact the study team |
| | | directly. Serious Adverse Event reports will also be handled by |
| | | the study management team which will contain allocation |
| 5 . 14 | A I I: I I | information. |
| Data Management | Not blinded | Data management staff will have access to the unblinded |
| | | datasets within the study randomisation system and database to |
| | | ensure data quality and to undertake central monitoring |
| CL d Claritation | Ni a i la li a al a al | activities. |
| Study Statistician | Not blinded | The study statistician and senior study statisticians will have |
| and Senior Study | | access to treatment allocations or data needed for generating |
| Statistician | | the Data and Safety Monitoring Committee (DSMC) closed |
| | | reports and the final analysis. They are also unblinded as they |
| Health Economist | Not blinded | generate the randomisation list. |
| Health Economist | Not billided | The study health economist and senior health economist will have access to treatment allocations for the final analysis. |
| Radiographic | Blinded | Radiographs will have the shaft and neck of the femur, along |
| | Dilliueu | with the lateral edge of the acetabulum, obscured to hide any |
| Assessor | | |
| | | residual changes resulting from surgery. |

18.2 Code break/ unblinding

Not applicable for this study.

19 SAMPLES

This study protocol does not involve any taking of new biological samples or any use of pre-existing samples.

20 IMAGES (RADIOGRAPHS)

This study will harvest routinely collected images of the hip/ pelvis available on the PACS taken preoperatively, post-intervention and the most recently collected at the three year post randomisation date. These routine images will be stored in a bespoke application (TRIAGE) hosted at the University of Oxford and will be used to quantify the degree of residual deformity by an independent assessor.

21 SAFETY REPORTING

21.1 Safety reporting period

Safety reporting for each participant will begin from randomisation and will end when the participant has reached their final main follow-up time point, at 36 months post-randomisation.

21.2 Definitions

Table 11: Definitions for safety reporting

| An adverse event | Any untoward occurrence in a clinical study participant. | | | |
|------------------|---|--|--|--|
| (AE) | Note : An AE can therefore be any unfavourable and unintended sign | | | |
| | (including an abnormal laboratory finding, for example), symptom or | | | |
| | disease temporarily associated with the study procedures, whether or not | | | |
| | considered related to the procedures. | | | |
| Related Adverse | An event that resulted from administration of any of the research | | | |
| Event | procedures | | | |
| Serious Adverse | An AE that: | | | |
| Event (SAE) | results in death | | | |
| | is life-threatening¹ | | | |
| | requires hospitalisation or prolongation of existing hospitalisation | | | |
| | results in persistent or significant disability or incapacity | | | |
| | is a congenital anomaly or birth defect; or | | | |
| | is otherwise considered medically significant by the Investigator² | | | |
| Unexpected | A serious adverse event related to the study (i.e. resulted from | | | |
| Related Serious | administration of any of the research procedures) and is unexpected (not | | | |
| Adverse Event | listed in the protocol as an expected occurrence). | | | |

 $^{^{1}}$ participant was at risk of death at the time of the event; it does not refer to an event which hypothetically might have caused death if it were more severe

A distinction is drawn between serious and severe AEs. Severity is a measure of intensity whereas seriousness is defined using the criteria above. Hence, a severe AE need not necessarily be serious.

21.3 Expected adverse events

This is a low risk, pragmatic trial where both of the study interventions are in common use. For this trial, foreseeable AEs will not need to be reported immediately, but will be recorded on participant and site reported CRFs. They include the following (including the need for hospital admission and/or further unplanned surgery to manage these complications in either group):

The complications anticipated in the management of these patients (particularly considering readmission or subsequent surgery) include pressure sores, non-union of the bone, wound or bone infection, major injury to nerves altering lower limb function, implant-related fracture, metalwork fracture/failure, need to remove/adjust metal implants, total hip arthroplasty (replacement).

² Medical events that may jeopardise the participant or may require an intervention to prevent one of the above characteristics/consequences.

21.4 Non-reportable AEs/SAEs

AEs that are unrelated to the intervention will not be reported. AEs deemed related to the intervention that do not meet the SAE definition and are not classed as foreseeable as per section 21.3 (such as discomfort during performance of exercises), will also not be reported.

21.5 Procedure for collecting safety events from sites/participants

These events will be recorded on patient-reported questionnaires and by the site investigators in the 'Complications' CRF if they become aware of such an event.

21.6 Reporting of SAEs from sites to the central study team

Only unexpected SAEs potentially related (possibly, probably, or definitely) to the study intervention/any of the research procedures will be reported immediately to the central study team. Such events will be reported immediately to the central study team as follows:

SAEs will be reported by the site research team using the SAE form within the REDCap study database within 24 hours of becoming aware of the event. The CTU is automatically notified of the SAE report through the database.

A paper SAE form will be used as a back-up if the SAE form is not available electronically. This must be emailed to [contact] within 24 hours of becoming aware of the event. The central study team will acknowledge receipt of any SAEs reported via email within one working day and provide the site with a unique SAE Log number.

21.7 Assessment of SAEs by the Principal Investigator (or delegate)

The PI at site (or delegated individual) is responsible for assessing all reported SAEs for seriousness, causality and expectedness.

21.7.1 Relatedness/causality

The assessment of "relatedness" to the study intervention is the responsibility of the PI at site or an agreed designee according to the following definitions:

Table 12: Relatedness of safety events

| Relationship to intervention | Attribution (Causality) | Description |
|------------------------------|-------------------------|----------------------------------|
| Unrelated | Unrelated | The AE is clearly NOT related |
| | | to the intervention |
| | Unlikely | The AE is doubtfully related to |
| | | the intervention |
| Related | Possible | The AE may be related to the |
| | | intervention |
| | Probable | The AE is likely related to the |
| | | intervention |
| | Definite | The AE is clearly related to the |
| | | intervention |

21.9 Review of SAEs by the Sponsor/CTU Nominated Person

An appropriately qualified person will review the SAE and raise any queries with the reporting site. If the site has not provided an assessment of causality and has not responded to the query, it will be assumed that the event reported is related to the study procedures/intervention. The site will be encouraged to respond and if a response is not provided the CI will be consulted by the CTU and the CTU will complete the Sponsor part of the SAE report.

21.10 Reporting of SAEs to the Research Ethics Committee (REC)

.All SAEs that are assessed as related and unexpected will be submitted to the REC within 15 days of the CTU/Sponsor becoming aware of the event.

21.11 Unblinding of SAEs for reporting to the REC

PI at site not unblinded, CI to be unblinded for SAE review.

21.12 Follow-up of Serious Adverse Events

If the SAE is an unexpected related event then follow up information must be provided as requested by the central study team. A follow-up report must be completed when the SAE resolves, is unlikely to change, or when additional information becomes available.

22 PREGNANCY

If a participant becomes pregnant during their participation in the study, it does not need to be reported due to the nature of the intervention as concluded in the risk assessment of the study.

23 STATISTICAL CONSIDERATIONS

23.1 Statistical Analysis Plan (SAP)

The statistical aspects of the study are summarised here with details fully described in a statistical analysis plan (SAP) that will be drafted early in the study and finalised prior to the final analysis data lock, or any planned interim comparative analyses. The SAP will be written by the Study Statistician in accordance with the current OCTRU SOPs. The Trial Steering Committee (TSC) and Data & Safety Monitoring Committee (DSMC) will review and, if necessary, provide input into the SAP.

23.2 Sample Size/Power calculations

172 participants providing data on the PROMIS Mobility Score for children at three years post randomisation (86 in each group) will provide 90% power to detect a difference in means of 5, assuming the standard deviation (SD) is 10 using a two group t-test with a 5% (2-sided) significance level. This is inflated to 216 participants (108 per arm) to allow for 20% attrition.

Raw scores of the PROMIS are translated into standardised T-scores with a population mean of 50 and an SD of 10.

The minimum clinically important difference (MCID) of PROMIS paediatric measures is generally 3.0-5.0 [29,30].

We discussed with children and families the size of the difference they would require to justify surgery, over optimised non-surgical containment. Given that surgery is a considerable intervention in the lives of the child and their family (i.e., the anaesthetic, the pain and scar, admission to hospital, the frequency of the requirement for a second procedure to removal metalwork, along with the lengthy

duration of immobilisation and recovery), families believed that the effect sought should be at the upper range of the MCID. Other studies have similarly highlighted that patients often seek greater effect sizes to warrant bigger surgical interventions than the established MCID [31].

23.3 Description of Statistical Methods

Reporting of results will be in accordance with the CONSORT Statement and relevant extensions [36, 37] [38].

It is anticipated that all statistical analysis will be undertaken using Stata (StataCorp LP, www.stata.com) or other validated statistical software tools.

23.3.1 Primary outcome

The PROMIS Mobility Score for Children at 3 years post-randomisation is the primary outcome of the trial. The primary analysis will use a linear regression model that adjusts for the baseline score and treatment group. As recommended by ICH E9 [39], the model will also adjust for the minimisation factors as fixed effects. An unadjusted analysis, that does not include the baseline score and minimisation factors, will also be performed.

23.3.2 Secondary outcome(s)

Continuous secondary outcomes measured over time (PROMIS Mobility over time, Wong-Baker Faces Pain Scale, CHU-9D and PROMIS Family Relationships) will be compared using a multi-level mixed effects linear regression model with repeated measures (level 1) grouped within participants (level 2). Models will include treatment, baseline score, time-by-treatment interaction and minimisation factors as fixed effects. Educational participation will be analysed as total days missed during the 3 year follow up using a Negative Binomial regression model, adjusting for treatment and minimisation factors as fixed effects. Degree of residual deformity will be analysed as Stulberg grade at 3 years follow up using an ordinal logistic regression model, adjusting for treatment and minimisation factors as fixed effects. The number and proportion of participants experiencing each type of complication will be summarised by treatment group. Heterogeneity by centre will be explored visually using forest plots and with a sensitivity analysis on the primary outcome where statistical models applied will also adjust for centre as a random effect.

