9.4 Secondary objectives and outcome measures

Table 7: Secondary objectives and outcome measures

| Objective | Outcome measure | Time point(s) of evaluation of this outcome measure (if applicable) | Data required | Source data (including location) |
|---|---|--|--------------------------------------|--|
| To compare lower extremity function in both groups | PROMIS Mobility CAT | Baseline and 3, 6, 9, 12, 18, 24, 30 and 36 months post randomisation | PROMIS mobility score | Case report Form (entered directly into the REDCap study database) |
| To compare pain levels in both groups | Wong Baker Faces Pain Scale | Baseline and 3, 6, 9, 12, 18, 24, 30 and 36 months post randomisation | Wong Baker Faces Pain Scale score | Case report Form (entered directly into the REDCap study database) |
| To compare Quality of Life, Activities of Daily Living, Sleep and Psychological Impact in both groups | CHU-9D Questionnaire | Baseline and 3, 6, 9m 12, 18, 24, 30 and 36 months post randomisation | CHU-9D score | Case report Form (entered directly into the REDCap study database) |
| To compare impact on family life in both groups | PROMIS family relationships tool | Baseline and 3, 6, 9, 12, 18, 24, 30 and 36 months post randomisation | PROMIS family relationships score | Case report Form (entered directly into the REDCap study database) |
| To compare educational participation in both groups | Non validated questionnaire on school absence | 3, 6, 9, 12, 18, 24, 30 and 36 months post randomisation | Days of school absence | Case report Form (entered directly into the REDCap study database) |

| Objective | Outcome measure | Time point(s) of evaluation of this outcome measure (if applicable) | Data required | Source data (including location) |
|---|--|--|--|--|
| To compare the complication rate, particularly considering the need for future operative interventions in both groups | Non validated questionnaire on complications | 6, 12, 18, and 36 months post randomisation | Frequency of pressure sores, non-union of the bone, wound or bone infection, major injury to nerves altering lower limb function, implant-related fracture, metalwork fracture/failure, need to remove/adjust metal implants, total hip arthroplasty (replacement) | Case report Form (entered directly into the REDCap study database) Medical notes |

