PROMIS Pediatric Family Relationships [25] - This has been highlighted as an important outcome within the core outcome set. The complex role of families in child and adolescent health and their role in the management of chronic conditions however has been hampered by a lack of validated measures of family relationship experiences. This instrument addresses this gap, with item banks and short forms developed using a rigorous mixed-method approach consistent with PROMIS standards.

Educational participation - Parents will be asked to indicate the number of days their child did not participate in educational activities due to their Perthes' disease.

Complications - All complications related to the disease and its treatment will be recorded. The complications anticipated in the management of these patients (particularly considering readmission or subsequent surgery) include pressure sores, non-union of the bone, wound or bone infection, major injury to nerves altering lower limb function, implant-related fracture, metalwork fracture/failure, need to remove/adjust metal implants, total hip arthroplasty (replacement).

Resource use - Participants' use of primary, secondary and community care services, as well as medications will be collected using a bespoke electronic resource use questionnaire. In addition, parental absence from work and additional days of purchased childcare will be collected.

Radiographs - This study will harvest routinely collected images of the hip/ pelvis available on the Picture Archiving and Communication System (PACS) taken pre-operatively, post-intervention and the most recent at 3 years post randomisation. These routine images will be stored in a bespoke application (TRIAGE) hosted at the University of Oxford and used to quantify the degree of residual deformity by an independent assessor, using the Stulberg classification for all hips in the Waldenstrom 3B (late re-ossification) or 4 (healed) stage of disease.

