13.4 Measures to reduce the potential for cross-overs

The OP Non-STOP study team strengthened their understanding of this issue through qualitative interviews with patients, parents and clinicians [33, 34]. It is anticipated that there will be similar numbers of cross-overs in both directions.

Despite an in-depth consent discussion, after randomisation to the surgery group, some parents, in consultation with their treating clinicians, will choose not to have surgery. Likewise, other families allocated to active containment, in consultation with their treating clinicians, will choose to undergo surgery. The most appropriate course of treatment will be available for participants at all times, e.g. participants can transition between groups, or, if requested, be withdrawn from the study. We will monitor cross-overs closely (on a site-by-site basis) to identifytrends that emerge, and disseminate learning points gleaned throughout the study.

To minimise cross-overs, the OP Non-STOP study team will provide a package of information to sites, built on our learning and previous work with the QuinteT group [35], to ensure that the language clinicians use is optimised.

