23.4 Inclusion in analysis

The principal analysis will be performed on the intention to treat population, analysing participants with available outcome data in their randomised groups, regardless of adherence.

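### The one stated complications summary is by arm, so with the two-way cross-over the protocol expects it does not give the risk per operated child; a descriptive table by treatment received would

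*Protocol*

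**What the plan says.** **Objective.** Section 9.4 (Table 7) sets the aim: "To compare the complication rate, particularly considering the need for future operative interventions in both groups".

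**What is counted.** Section 9.5 lists "pressure sores, non-union of the bone, wound or bone infection, major injury to nerves altering lower limb function, implant-related fracture, metalwork fracture/failure", and then removal or adjustment of metal implants and total hip arthroplasty. Section 21.3 gives the same list as the foreseeable adverse events.

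**How it is summarised.** Section 23.3.2 states: "The number and proportion of participants experiencing each type of complication will be summarised by treatment group". It gives no model, no test and no summary by treatment received.

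**Population.** Section 23.4 states: "The principal analysis will be performed on the intention to treat population, analysing participants with available outcome data in their randomised groups, regardless of adherence". The protocol defines no safety or as-treated population.

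**Cross-over.** Section 13.4 says that "after randomisation to the surgery group, some parents, in consultation with their treating clinicians, will choose not to have surgery", that "other families allocated to active containment, in consultation with their treating clinicians, will choose to undergo surgery", and: "It is anticipated that there will be similar numbers of cross-overs in both directions". It gives no rate. It plans measures to limit cross-over and monitoring of it by site.

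**Data held.** The surgery form in Appendix 2 records the date of surgery, the operation type and intra-operative complications.

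**The concern.** Most of the listed complications differ from the trial's other outcomes in one respect: they need an operation or an implant. Non-union, wound infection, implant-related fracture, metalwork failure and implant removal all belong here. For such events a by-arm table does two things when children cross over. Children allocated to surgery who decline it remain in the surgery denominator. Children allocated to active containment who are operated on place their operative complications in the active containment column. Both shrink the visible difference, which is the less cautious direction for a harms table.

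The reader who needs a different figure is the family deciding on an operation. Section 23.2 reports that families weighed surgery by its burdens, a second procedure to remove metalwork among them. Their question is what happens to a child who is operated on, and no stated output answers it. The complications summary also carries most of the surgical harm data. Under sections 21.3, 21.4 and 21.6, foreseeable events go only onto case report forms, other related non-serious events are not reported, and only unexpected and potentially related serious events are reported at once.

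**Working it through.** **What treatment group means.** Section 15.3 uses the term for the two groups balanced by minimisation, section 23.3.1 enters it as the term in the primary model, and section 23.4 speaks of randomised groups. Randomised arm is therefore the natural reading in section 23.3.2, though it is an inference.

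**Plan's own figure.** There is none to reproduce: the protocol gives no complication rate and no cross-over rate. Its only power calculation concerns the primary outcome and has no bearing here. The arm size, 108, is from section 10.

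**Assumed inputs**
- c: share crossing over in each direction. Equal shares follow from section 13.4 with 1:1 allocation; the values 5% to 30% are assumed.
- pS: risk of a listed complication if operated, assumed 20%.
- pA: risk if never operated, assumed 0%, then 2% as a check.
- Crossing over is unrelated to complication risk.

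**Formulas**
- Surgery arm: (1 − c)·pS + c·pA
- Active containment arm: c·pS + (1 − c)·pA
- Between-arm difference: (1 − 2c)·(pS − pA)

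**Results with pS = 20%, pA = 0%.** By treatment received the figures would be 20% v 0%, a difference of 20 points.

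| c | Surgery arm | Active containment arm | Difference (points) | Shrinkage |
|---|---|---|---|---|
| 5% | 19% (20.5 of 108) | 1% (1.1 of 108) | 18 | 10% |
| 10% | 18% (19.4 of 108) | 2% (2.2 of 108) | 16 | 20% |
| 20% | 16% (17.3 of 108) | 4% (4.3 of 108) | 12 | 40% |
| 30% | 14% (15.1 of 108) | 6% (6.5 of 108) | 8 | 60% |

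**Check with pA = 2%, c = 20%.** Surgery arm: 0.8 × 20% + 0.2 × 2% = 16.4%. Active containment arm: 0.2 × 20% + 0.8 × 2% = 5.6%. The difference is 10.8 points against 18 by treatment received, a ratio of 0.60, as before. The proportional shrinkage depends only on c and was the same for pS of 10%, 20% and 30%.

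**The case against.** The strongest reply is that nothing in section 23.3.2 is wrong. Section 23.1 leaves full detail to a statistical analysis plan that is not at hand, and supplementary safety tables often sit there. The protocol names one summary and excludes no other. A by-arm table is also the randomised comparison and suits the Table 7 objective: an operation after allocation to active containment, and its complications, are consequences of that policy. All of this stands. It is why the by-arm table should stay, and why this is an improvement and not a correction.

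Several stronger readings are tempting but not supported:
- *That an intention-to-treat rule is laid down for complications.* The sentence in section 23.4 is about the principal analysis and does not mention complications.
- *That all the listed events follow only an operation.* Pressure sores and total hip arthroplasty can occur without containment surgery; section 8.1 links hip replacement to the disease itself. Zero risk in unoperated children is thus a simplification, though the shrinkage factor does not depend on it.
- *That active containment is wrongly charged with operative events.* That holds only if the target is risk per operation, which the protocol does not set as its objective.
- *That the data monitoring committee would see a weakened signal.* No text says how its reports are laid out. Section 26.4.2 gives it all safety data, and Table 10 leaves the statisticians unblinded.

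A table by treatment received has biases too. Section 13.4 has cross-over decided with the treating clinician, so it may follow prognosis. Grouping by surgery at any time would also credit events before a late operation to the operated group unless they are separated.

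**Conclusion.** The point holds as a cheap improvement. The by-arm summary is valid for what it estimates, but no output stated in the protocol gives the complication risk in children who were operated on, while the protocol expects cross-over both ways and most listed complications need surgery or an implant. Under symmetric cross-over unrelated to risk, the between-arm difference is (1 − 2c) of the operated-versus-unoperated difference. The direction follows whenever operated children carry the higher risk. The size for this trial cannot be derived from the protocol: it could be slight (19% v 1% in place of 20% v 0% at c = 5%) or large (14% v 6% at c = 30%). If crossing over depends on prognosis, the factor is only approximate. A reader should not infer that the by-arm table is an error or that surgical harm would be hidden: in every case above the surgery arm still shows the higher rate.

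**What to change.** In section 23.3.2, keep the by-arm summary and add one descriptive table:
- each complication by treatment received, any containment surgery versus never operated, with those children as denominators;
- cross-over counts in each arm beside it;
- intra-operative complications from the surgery form included;
- in the operated group, operative complications counted from the date of surgery, and events before surgery shown separately;
- a label stating that the groups are self-selected and the comparison is not randomised.

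Supplying the same table to the data monitoring committee is a suggestion only.

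The cost is one table from data already collected. The primary analysis, sample size and visit schedule do not change. The downside is that readers may take the table as causal, which the label and the adjacent by-arm table are there to prevent. Fixing it before comparative results are seen also avoids the charge of choosing it afterwards.

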23.7 Level of Statistical Significance

All comparative outcomes will be presented as summary statistics and reported together with 95% confidence intervals and all tests will be carried out at a 5% two-sided significance level.

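### Table 7 aims to compare the complication rate and further operations between arms, but section 23.3.2 specifies only a by-type summary, from which no overall rate can be derived

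*Protocol*

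**What the plan says.** Table 7 in section 9.4 lists complications as a secondary outcome with the objective "To compare the complication rate, particularly considering the need for future operative interventions in both groups". They are collected at "6, 12, 18, and 36 months post randomisation". Section 9.5 says that the anticipated complications "include pressure sores, non-union of the bone, wound or bone infection, major injury to nerves altering lower limb function, implant-related fracture", and then adds metalwork fracture or failure, removal or adjustment of implants, and hip replacement. That makes eight named types, and section 21.3 repeats them.

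Section 23.3.2 gives the analysis: "The number and proportion of participants experiencing each type of complication will be summarised by treatment group". The same section names a between-arm model for PROMIS Mobility over time, pain, CHU-9D, family relationships, educational participation and Stulberg grade; the last is analysed "using an ordinal logistic regression model, adjusting for treatment and minimisation factors as fixed effects".

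Section 23.7 adds a general rule: "All comparative outcomes will be presented as summary statistics and reported together with 95% confidence intervals". It does not say whether complications count as a comparative outcome, or on what scale they would be compared.

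**The concern.** The objective speaks of a complication rate and singles out further operations. The stated analysis produces neither quantity. A child with a wound infection who later has an implant removed is counted in two rows, so the rows cannot be added up to a number of children. No row is defined for further surgery as such.

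This matters because harm is half of the decision the trial is meant to inform. Section 5 presents avoidance of surgical risk as the main argument for active containment. Section 23.2 explains that families wanted a difference at the upper end of the MCID range because of the burden of surgery, including second procedures. As the plan stands, benefit is reported as an adjusted difference with an interval, whereas harm is reported as a list with no specified overall contrast to set against it.

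**Working it through.** **Plan's own figure.** The protocol gives no expected complication rate, so there is none to reproduce. Its sample size supplies the arm sizes used below. Section 23.2 says 86 per arm "will provide 90% power to detect a difference in means of 5" with SD 10. The two-sample t-test calculation gives 85.03 per arm, rounded up to 86, with power 90.3%. Inflating for 20% attrition gives 86 / 0.8 = 107.5, so 108 per arm and 216 in total. The stated figure reproduces.

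**Can the overall rate be derived from the by-type rows?** Let n_i be the number of children with type i among N in an arm. The number with any complication lies between the largest n_i (complete overlap) and the smaller of N and the sum of the n_i (no overlap).

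Inputs: eight types (sections 9.4, 9.5, 21.3), N = 108 (section 23.2), and n_i = 3 for each type (an assumption for illustration).
- Complete overlap: 3 children, 3/108 = 2.8%.
- No overlap: 8 × 3 = 24 children, 24/108 = 22.2%.

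Both give the same by-type table. If the other arm had no events, the overall risk difference could be anywhere from 2.8 to 22.2 points. In percentage terms, using 1 − (1 − p)^8 for independence:

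| Each type | Full overlap | Independent | No overlap |
|---|---|---|---|
| 2% | 2% | 15% | 16% |
| 3% | 3% | 22% | 24% |
| 5% | 5% | 34% | 40% |

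These are logical bounds. Complete overlap of all eight types is not realistic, but the table itself does not say where between the bounds the truth lies.

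**Would an overall contrast be informative at this size?** For a risk difference d = p1 − p2, the simple 95% interval is d ± 1.96 × √[p1(1 − p1)/n + p2(1 − p2)/n]. The risks are assumptions. For 20% v 5% with n = 108: √[(0.16 + 0.0475)/108] = 0.0438, half-width 8.6 points.

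| Assumed risks | Difference (95% CI), 108 per arm | Half-width, 86 per arm |
|---|---|---|
| 10% v 5% | 5 (−2.0 to 12.0) | 7.8 |
| 20% v 5% | 15 (6.4 to 23.6) | 9.6 |
| 20% v 10% | 10 (0.6 to 19.4) | 10.6 |
| 30% v 10% | 20 (9.7 to 30.3) | 11.6 |

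So the overall difference can be estimated to within roughly 7 to 12 points.

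**Why a score-based interval when events are few.** For 3 v 0 of 108 the simple formula gives 2.8 ± 3.1, that is −0.3 to 5.9 points. It takes no account of uncertainty in the arm with no events. The Newcombe score-based interval is −1.1 to 7.9.

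**The case against.** Four points can be made in the plan's defence.

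- **Section 23.7 may already cover it.** Read with the comparative objective in Table 7, it can fairly be taken to promise an interval for each type. A reader might infer from 23.3.2 that no between-arm difference will be estimated at all. The documents do not support that; what they show is that none is specified. Section 23.7 still defines no overall rate, no further-surgery endpoint and no effect measure.
- **This is ordinary SAP detail.** Section 23.1 calls the protocol text a summary, and a SAP may add an overall row. But the protocol is not silent here: it fixes an analysis that does not match its own objective, and the mismatch is between two statements in the same document.
- **By-type reporting suits these data.** Implant-related fracture, metalwork failure and implant removal need an implant, and non-union needs a cut bone. Children allocated to active containment can have these essentially only after crossing over. A significance test on a composite would largely show that operated children have metalwork. This stands, and it limits how the composite may be used.
- **Single rows may be informative.** A reader might infer that every listed type is so rare that no row could separate the arms, and that only a composite could. That needs all eight types to be equally rare. Section 23.2 cites the frequency of second procedures for metalwork removal, which is one of the eight types. No rate is given, but if that row alone were 10% v 0.5%, power would be about 90% at 108 per arm and 77% at 86. The case for an overall rate therefore does not rest on power.

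**Conclusion.** The mismatch is real. The objective is to compare the complication rate, with emphasis on further operations. The stated analysis yields proportions by type and arm, from which neither quantity can be recovered. The size of the gap is shown by the 3-to-24-children example; it rests only on the list of eight types, 108 per arm and an illustrative count of 3 per type. The precision figures rest on assumed risks that the protocol does not give.

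It would go too far to say that the objective is left wholly unanswered: proportions by arm for each type are a comparison, though not of an overall rate. The point is modest. It concerns one secondary safety outcome and leaves the primary analysis and sample size untouched. It is worth making because the repair is cheap and uses data already planned.

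**What to change.** In section 23.3.2, after the sentence on complications, state that two proportions by 36 months will each be compared between randomised arms as a risk difference with a 95% confidence interval, using a score-based interval if events are few:

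- (a) participants with at least one listed complication;
- (b) participants having further, unplanned or subsequent hip surgery beyond the allocated index procedure.

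The definition of (b) should say how planned metalwork removal is counted, and how containment surgery is counted in a child allocated to active containment, since section 13.4 expects cross-overs. Keep the by-type table beside both results. Present them as estimates and say that no hypothesis test is planned on them, because section 23.7 otherwise implies that "all tests will be carried out at a 5% two-sided significance level".

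The cost is a sentence or two and two further analyses. The complication forms are already scheduled to 36 months, and section 21.3 already has further unplanned surgery recorded; whether the forms also capture planned second procedures should be checked. The downside is that the composite mixes events of unequal gravity and is structurally one-sided, so it must not be quoted without the breakdown.

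If the investigators prefer not to add these contrasts, rewording the Table 7 objective as descriptive would remove the inconsistency, but it would leave the overall rate and further surgery unreported.
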